Postoperative complications cause significant morbidity in post cardiac surgery patients. The PRP has been proposed in clinical trials to reduce the frequency of complications in patients undergoing median sternotomy for cardiac operative procedures. The purpose of our study is to evaluate whether there is any beneficial effect of use of PRP in addition to standard care after on pump CABG, cardiac surgery.

Research Question

Does application of PRP after CABG, cardiac surgery reduce the frequency of sternal wound complications?

Objective

To compare the complication rates of application of PRP in addition to standard sternal wound closure versus standard sternal wound closure alone.

Population

All consecutive patients of age 45 to 72, undergoing CABG, cardiac surgery with median sternotomy will be included in the study.

Intervention

Application of 6 mL of autologous PRP to sternum and soft tissue during sternal closure.

Comparison

The control group will undergo midline sternotomy with a sternal saw blade. The sternum will be closed with a simple interrupted or figure of eight stainless steel wire. The wounds will be closed in a layered manner with absorbable suture and dressed with Steri-Strips, gauze and paper tape. The study group will additionally receive 6 mL of autologous PRP applied to sternum and soft tissue during sternal closure.

Outcome

(i) Primary Outcome;

Primary outcome will be measured as frequency of sternal wound complications in terms of delayed healing, superficial infection, deep infections, and readmission rate including mediastinitis in 30-days period post-surgery.

(ii) Secondary outcome;

Secondary outcome will be the overall cost burden for the 30-days post-surgery period.

(iii) Other outcomes;

Other outcomes will be ICU stay (days), blood transfusions more than 4 units and platelets transfusions more than 4 units within 30 days.

OPERATIONAL DEFINITIONS

1-Cardiac Surgery: Cardiac surgery, also called heart surgery, involves surgical operations performed on the heart to correct life-threatening conditions. The surgery can be either open-heart surgery or minimally invasive surgery depending on the condition to be corrected.

2-PRP: Platelet-rich plasma (PRP) is defined as a portion of the plasma fraction of autologous blood having a platelet concentration above baseline.

3-Study Outcome

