Study Outcome will be measured as frequency of sternal wound complications in terms of delayed healing, superficial infection, deep infections, and readmission rate including mediastinitis in 30-days period post-surgery. Secondary outcome will be the overall cost burden for the 30-days post-surgery period. Other outcomes will be ICU stay (days), blood transfusions more than 4 units and platelets transfusions more than 4 units within 30 days.

4- DSWI: DSWI diagnosis will be made, based on the guidelines of the CDC, in patients who developed one or more of the following: [1] positive culture of mediastinal tissue or fluid; [2] clinical evidence of mediastinitis during sternal reoperation; or [3] chest pain, sternal instability, purulent discharge from the mediastinum associated with a positive blood culture. DSWI presenting in the first 30 days after operation will be included in the study.

5- SWI: All the infections will be considered positive that will involve skin and subcutaneous tissue within the first 30 postoperative days, not reaching the sternum, requiring local surgical intervention with regular wound care, accompanied by antibiotic therapy and/or Vacuum Assisted Closure (VAC) therapy.

6- Delayed Healing: Healing is a complex biochemical process of tissue repair after it has been damaged. It has three stages which are inflammation, proliferation and remodelling. Delay in the specific time period or in the biochemical process is called delayed healing. Skin,

subcutaneous tissue or sternum which is unable to heal within two weeks of surgery will be considered delayed wound healing.

7- Readmission: It is defined as any hospital readmission within 30 days of discharge related to the index surgery.

8- ICU stay: Stay that refers to the duration, in days, spent in the intensive care unit, within 30 days postoperatively.

9- Blood transfusion: It is defined as the requirement of more than 4 units of packed red blood cells (PRBC) or platelets within 30 days postoperatively.

Hypothesis

Administration of platelet rich plasma during sternal wound closure reduces the frequency of complications in the 30-days post-surgery period.

MATERIAL AND METHODS

Study Design

Randomized control trial

Study Setting

The Department of Cardiac Surgery, Cardiac Center, Pakistan Institute of Medical Sciences (PIMS), Islamabad.

Duration

06 months after acceptance of synopsis

Sample selection;

Inclusion criteria

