Patients from 45 to 72 years of age, undergoing on pump CABG,

cardiac surgery with median sternotomy.

Patients who provide consent.

Exclusion criteria

- BMI less than **18.5** or more than **24.9**
- Bilateral harvesting of the internal mammary artery,
- Steroid therapy,
- Known Diabetic,
- Active smoker,
- Osteoporosis,
- Chronic lung disease,
- CPB time more than 72.5 minutes
- Platelet Rich Plasma cannot be obtained.
- Patients who are not candidates for blood bank donations.

Sample size

The sample size has been calculated by using WHO size calculator with the statistical assumptions as following:

(Level of significance = 5%), (Power of test = 80%), (Population standard deviation = 3.0)

(Anticipated population, rate of oedema and infiltration in prp group, P1= 18%)

Anticipated population, rate of oedema and infiltration in control group, P2= 44% Sample size comes out to be 49 cases in each study group and a total of 98 patients will be included in the study.

Sampling Technique

Participants will be recruited using non-probability consecutive sampling and randomly assigned to one of two groups.

Data Collection Procedure

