tissue during sternal closure. Participants and outcome assessors will be blinded to group assignment, while surgeons performing the procedure will be aware of the intervention

Primary outcome will be measured as frequency of sternal wound complications in terms of delayed healing, superficial infection, deep infections, and readmission rate including mediastinitis in 30-days period post-surgery. Secondary outcome will be the overall cost burden for the 30-days post-surgery period. Other outcomes will be ICU stay (days), red cell concentrate (RCC) more than 4 units and platelets transfusions more than 4 units.

All the information will be entered on the predesigned Performa by the researcher himself to comply with the study protocol attached as **Annexure-I**.

Data Analysis

Quantitative variables (age, hospital stay, ICU stay, cost) will be summarized as mean \pm SD or median (IQR) and compared using t-test or Mann-Whitney U test. Categorical variables (superficial/deep wound infections, delayed healing, readmissions, transfusion requirements, residence (urban\rural), education status and socioeconomic background (low\middle) will be reported as counts and percentages and compared using chi-square or Fisher's exact test. A p-value <0.05 will be considered significant. Missing data will be handled using complete case analysis. All analyses will be performed using [SPSS/R].

Ethical Considerations

From ethical point of view:

- Those patients will be included in the study that will be willing to participate in the study.
- A written informed consent will be taken from the patients and they will be ensured that their confidentiality will not be breached.
- There will be no compromise on the standard care and treatment for study purposes.

References

- [1] Reser, Diana, et al. "Median sternotomy." *Multimedia manual of cardiothoracic surgery: MMCTS 2015* (2015).
- [2] Balachandran, Sulakshana, et al. "Risk factors for sternal complications after cardiac operations: a systematic review." *The Annals of thoracic surgery* 102.6 (2016): 2109-2117.
- [3] Patel, Amit N., et al. "Evaluation of autologous platelet rich plasma for cardiac surgery: outcome analysis of 2000 patients." *Journal of cardiothoracic surgery* 11.1 (2016): 1-6.
- [4] Heilmann, Claudia, et al. "Wound complications after median sternotomy: a single-centre study." *Journal of cardiothoracic surgery* 13.1 (2018): 1-6.

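### Superficial infection is defined by the need for local surgical intervention, with no treatment-independent criterion, and unblinded surgeons are not excluded from that decision, so blinded assessment may not protect this primary outcome component

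*Protocol*

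**What the plan says.** The Outcome section of the protocol gives the primary outcome as "frequency of sternal wound complications in terms of delayed healing, superficial infection, deep infections, and readmission rate including mediastinitis" over 30 days, so superficial infection is one of its components.

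Operational Definitions, item 5, defines that component in one sentence. It starts with anatomy and timing: "All the infections will be considered positive that will involve skin and subcutaneous tissue within the first 30 postoperative days, not reaching the sternum". It then adds a treatment condition: "requiring local surgical intervention with regular wound care, accompanied by antibiotic therapy and/or Vacuum Assisted Closure (VAC) therapy". The and/or joins only antibiotics and VAC, so on a plain reading local surgical intervention is needed in every case. The item names no discharge, local sign or culture result.

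Item 4, on deep infection, is built differently. It rests on culture results, findings at reoperation, or symptoms with a positive blood culture.

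On blinding, Data Collection Procedure states: "Participants and outcome assessors will be blinded to group assignment, while surgeons performing the procedure will be aware of the intervention". The opening summary says the same. Neither place says who decides that a superficial infection needs intervention, on what threshold, or whether the operating surgeons may take part. On recording, Data Collection Procedure adds: "All the information will be entered on the predesigned Performa by the researcher himself".

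**The concern.** When the need for a treatment is part of the event definition, whatever influences the treatment decision also influences the event count. Here the people declared to know the group are surgeons, and the qualifying treatment is a surgical one. If that decision is made with knowledge of the allocation, the two arms can have the same infections and still differ in counted events. A blinded assessor who applies the definition correctly does not undo this, because the difference arose before the assessment.

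Two things are at stake. The first is a distorted comparison on a component of the primary outcome. The second is the loss of genuine superficial infections managed without surgery, in a trial of 98 patients. The analysis cannot recover infections that the definition never recorded.

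**Working it through.** **The plan's own figure.** The Sample size section gives 49 per arm for 18% versus 44%, at 5% significance and 80% power. With two-sided alpha, pooled variance under the null and no continuity correction, the mean rate is 0.31 and

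n = [1.96·√(2·0.31·0.69) + 0.842·√(0.18·0.82 + 0.44·0.56)]² / 0.26² = (1.282 + 0.528)² / 0.0676 ≈ 48.5, rounded up to 49.

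The figure reproduces and is not in dispute. The point concerns how events are ascertained, not how many patients are needed.

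**Inputs for the illustration.**
- 49 per arm and p < 0.05, from Sample size and Data Analysis.
- Test: Data Analysis allows chi-square or Fisher's exact test, so both are shown. It lists superficial infection among the variables to be compared, so the component is tested on its own here.
- True infection rate p, equal in both arms. The value 8% is the top of the 0.2 to 8% range for wound dehiscence and infection in the Introduction. The value 18% is an assumption. The same number appears under Sample size, but there it is a rate of oedema and infiltration, not of infection.
- Share of infections judged to need surgery and operated on: 90% in controls, and 90% (no bias), 70% or 50% on PRP. These shares are assumptions; the documents give none.

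**Step 1: counted rates.** The counted rate is p × share. The counted risk ratio is therefore the ratio of the shares, whatever p is: 0.70/0.90 = 0.78 and 0.50/0.90 = 0.56, with no true effect.
- At 8%: 7.2% in controls against 5.6% or 4.0% on PRP, or about 3.5 against 2.7 or 2.0 expected events.
- At 18%: 16.2% against 12.6% or 9.0%, or about 7.9 against 6.2 or 4.4 expected events.

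**Step 2: chance of a falsely significant result favouring PRP.** Sum Bin(c; 49, control rate) × Bin(t; 49, PRP rate) over all pairs with c > t and p < 0.05.

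| True rate | Test | 90% v 90% (no bias) | 90% v 70% | 90% v 50% |
|---|---|---|---|---|
| 8% | Pearson chi-square | 3.0% | 5.8% | 10.9% |
| 8% | Fisher | 0.6% | 1.3% | 2.6% |
| 18% | Pearson chi-square | 2.7% | 7.9% | 20.0% |
| 18% | Fisher | 1.2% | 3.8% | 10.6% |

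In every row the 70% share at least nearly doubles the no-bias figure. The absolute level depends heavily on the test and the true rate.

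**The case against.** The strongest reply is that none of this is shown to happen. The protocol does not say that operating surgeons make postoperative wound decisions, and the shares in the illustration have no source in it. Bias could also run the other way, for instance if PRP wounds were opened more readily. All of that stands, so the point is a risk that the plan leaves open and not a demonstrated bias.

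The size can also be pressed down. At an 8% rate the expected counts fall below 5, where Fisher's test is the usual choice, and the false-positive chance then stays at or near 2.5% even with a strong imbalance. If Fisher's test is used only when an expected count is below 5 (an assumed rule), the 8% figures are 1.8% and 3.2%, against 1.1% without bias. With a milder 90% versus 80% split, that rule gives 1.4% at 8% and 4.6% at 18%. This also stands for significance testing. It does not touch the distorted risk ratio.

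The definition speaks of infections that require intervention, not of infections that received it. A blinded assessor could in principle judge the need. That is fair, and a reader who infers that the assessor can do no more than note whether an operation took place goes too far. But the protocol gives the assessor no criteria for such a judgement, so the recorded treatment is the likely guide.

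Some infections managed without surgery may still enter the primary outcome as delayed healing if the wound is unhealed at two weeks (item 6). The loss of events is therefore partial, and it cannot be quantified.

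A reader might also infer that one unblinded researcher enters allocation and outcomes together on a single form. The text does not support that. It does not state whether the researcher is blinded, and the form's layout (Annexure-I) is not in the text reviewed.

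**Conclusion.** The point holds as a weakness in the definition of one component of the primary outcome. As written, the rule makes a treatment judgement a condition of the event, offers no criterion independent of treatment, and leaves unblinded surgeons free to take part in that judgement. Blinded assessment therefore does not secure this component. Infections managed without surgery are not counted as superficial infection.

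Neither the size nor the direction of the bias can be derived from the documents. The risk ratios of 0.78 and 0.56, and the error rates in the table, rest wholly on the assumed intervention shares. At the rate closest to the protocol's own background range, the false-positive effect is material by Pearson chi-square and small by Fisher's test. Much larger error rates could be obtained by putting the 44% from the Sample size section in as an infection rate, but that figure describes oedema and infiltration and does not support such a use. If a combined outcome were tested instead of the component, the effect would also depend on the other components. The change is cheap and is worth making before outcomes are collected.

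**What to change.** For outcome counting only, define superficial infection by findings: infection of skin or subcutaneous tissue, not reaching the sternum, within 30 days of surgery, shown by prespecified wound signs or purulent drainage. Treat a positive culture as supporting evidence but do not require it, since taking a culture is itself a clinician's decision. Have the blinded assessor judge the event whatever treatment was given, and record the judgement without sight of the allocation.

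Keep the need for local surgical intervention as a severity grade, and report the protocol's present treatment-based definition as a sensitivity analysis.

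The cost is a reworded definition, a short list of signs, and a way of recording the outcome that does not show the group. Blinded assessors are already planned. The downside is that milder infections are counted too; the severity grade keeps them distinguishable. The sample size formula is not affected, and patient management does not change.

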Over a period of six months, all consecutive consenting patients undergoing on pump coronary bypass grafting surgery requiring sternotomy will be enrolled. The patients will be randomized into two groups. The control group will receive standard of care sternal closure. The study group will receive standard of care sternal closure plus PRP applied to the sternum and the surrounding tissue at the time of closure. Participants and outcome assessors are blinded to group assignment, while surgeons performing the procedure are aware of the intervention. The patients will be followed up for a period of 30 days post-surgery. Wound healing, deep and superficial infection including mediastinitis, and readmissions within 30 days will be documented as primary outcomes. Secondary outcome will be the overall cost burden for the 30-days post-surgery period. Other outcomes will be ICU stay (days), blood transfusions more than 4 units and platelets transfusions more than 4 units.

Discussion

Wound dehiscence and infection in post cardiac surgery period are a significant source of morbidity and mortality. Treatment of these complications may cause prolonged hospitalization, prolonged antibiotic therapy, and revisions of operative procedures. In addition to burden on physical health, the complications associated with cardiac surgery can portend a high financial cost to the patient. The PRP has been shown to decrease the incidence of sternal wound complications following cardiac surgery and routine use of platelet rich plasma has been advocated for all patients undergoing sternotomy for cardiac surgical procedures.

Keywords

Sternal wound infection, Superficial sternal wound infection, Deep sternal wound infection, Surgical site infection, Delayed wound healing, Median sternotomy, Cardiac surgery, Postoperative wound complications, Hospital length of stay, Cost analysis, Platelet rich plasma, coronary artery bypass grafting, wound healing, CABG, readmission rate

INTRODUCTION

Median sternotomy in cardiac surgery is considered to be the gold standard incisional approach for the majority of cardiac operative procedures resulting in a low failure rate and excellent long-term outcomes [1].

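### Delayed healing, a primary-outcome item, counts a sternum not healed at two weeks as an event, but the protocol gives no observable criterion for a healed sternum

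*Protocol*

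**What the plan says.** The protocol's Outcome section gives the primary outcome as the "frequency of sternal wound complications in terms of delayed healing, superficial infection, deep infections, and readmission rate", including mediastinitis, over 30 days. The same list returns under Study Outcome and in Data Collection Procedure.

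Operational Definitions, item 6, defines delayed healing. It first describes healing as a biochemical process: "It has three stages which are inflammation, proliferation and remodelling". It then sets the rule. Skin, "subcutaneous tissue or sternum which is unable to heal within two weeks of surgery will be considered delayed wound healing". The tissues are joined by 'or', so any one of them is enough.

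On timing, the abstract says "The patients will be followed up for a period of 30 days post-surgery". On assessment, Data Collection Procedure says "Participants and outcome assessors will be blinded to group assignment" and that data go on a predesigned form, Annexure-I, which is not in the text at hand. No visit dates, imaging, stability test or wound score appear in the protocol text.

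**The concern.** One deadline covers skin, soft tissue and a bone that the protocol says is divided with a saw and closed with steel wire. The definition describes healing as running through to remodelling but does not say what finding marks a tissue as healed. For skin and subcutaneous tissue an assessor can fall back on what is visible. For the sternum the text offers nothing to look at.

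That leaves two ways to score the clause:

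- **Literally.** Any sternum whose repair is incomplete at 14 days is an event. This could include many patients in both arms whether or not they received PRP.
- **By judgement.** Each assessor decides when to apply the clause, and the event rate depends on who assesses.

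In both cases events unrelated to treatment, or inconsistently recorded, enter an item of the primary outcome and shrink the difference between arms that the trial is meant to detect.

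**Working it through.** **1. The definitions side by side.** The neighbouring infection definitions show what is missing from item 6.

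| Item | What makes it an event | Observable as written? |
|---|---|---|
| Deep infection (definition 4) | Positive mediastinal culture; mediastinitis seen at reoperation; or chest pain, instability and purulent discharge with a positive blood culture | Yes |
| Superficial infection (definition 5) | Depth limited to skin and subcutaneous tissue, plus the treatment required | Yes |
| Delayed healing (definition 6), skin or subcutaneous | Not healed at two weeks | Partly: can be inspected, but 'healed' is undefined |
| Delayed healing (definition 6), sternum | Not healed at two weeks | No criterion and no assessment described |

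**2. The plan's own sample size.** Inputs from the Sample size section: 18% with PRP, 44% in control, "Level of significance = 5"%, power 80%, 49 per arm. Sidedness is not stated; two-sided is assumed. With the pooled-variance formula and no continuity correction,

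n = [1.960 × √(2 × 0.31 × 0.69) + 0.842 × √(0.18 × 0.82 + 0.44 × 0.56)]² / 0.26²

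= (1.282 + 0.528)² / 0.0676 = 48.5, rounded up to 49.

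The stated 49 per arm is reproduced. The two rates are described as oedema and infiltration, so they say nothing about how often delayed healing would occur.

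**3. Illustration of dilution.** Let a share q of patients in both arms meet the sternum clause regardless of treatment, and let the rest keep the planning rates:

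- PRP: p1 = q + (1 − q) × 0.18
- Control: p2 = q + (1 − q) × 0.44
- Difference: p2 − p1 = (1 − q) × 0.26

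Power is exact: the binomial probabilities of all outcomes with a Pearson chi-square p-value below 0.05, with 49 per arm.

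| q (assumed) | PRP | Control | Difference | Power |
|---|---|---|---|---|
| 0 | 18.0% | 44.0% | 26.0 points | 80.7% |
| 0.10 | 26.2% | 49.6% | 23.4 points | 67% |
| 0.25 | 38.5% | 58.0% | 19.5 points | 51% |
| 0.50 | 59.0% | 72.0% | 13.0 points | 27% |

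A normal approximation gives nearly the same values (80.4% at q = 0, 49% at 0.25, 27% at 0.50).

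The table shows how sensitive a comparison of this size is to non-specific events. It does not predict power for this outcome: q is assumed, the base rates belong to another endpoint, and q is taken as equal in both arms.

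**The case against.** **Most or all patients would be events.** A reader might infer this from the literal wording. The protocol gives no sternal healing time, so it cannot be shown from the document. The Introduction cites sternal complications in 0.4% to 8% of patients, which suggests the authors meant clinical wound failure. This objection stands: the share is unknown. It also shows that the wording and the probable intent differ, which is a reason to correct the wording.

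**The criterion cannot be observed at all.** This too would be too strong. Day 14 lies inside the 30-day follow-up, blinded assessors are named, skin and soft tissue can be inspected, and Annexure-I may carry dates and wound items. What can be said is that the protocol text describes no assessment of sternal healing.

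**The infections and readmissions would be swamped.** Data Analysis lists infections, delayed healing and readmissions as separate categorical variables, and the abstract speaks of primary outcomes in the plural. If each item has its own test, a poorly defined delayed-healing item damages only its own comparison. The Outcome section can also be read as one frequency of complications, so dilution of the whole primary outcome is conditional on a composite analysis.

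**The power figures do not belong to this outcome.** Correct. The Introduction also says PRP growth factors can improve bone healing, so q need not be equal in the two arms. The figures remain useful only as an illustration of dilution.

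None of these objections supplies a criterion for a healed sternum, and blinding the assessor does not create one.

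**Conclusion.** The point holds as a defect in a stated rule. Definition 6 makes an unhealed sternum at two weeks sufficient for a primary-outcome event and gives no observable criterion for it, unlike the two infection definitions beside it. The clause will produce either non-specific events in both arms or assessor-dependent ones. The delayed-healing comparison is weakened in any case; the whole primary outcome is weakened only if it is analysed as a composite.

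The size cannot be fixed from the protocol. Under the illustrative assumptions, even a 10% share of non-specific events costs about 14 points of power (80.7% to 67%). This should be corrected before outcomes are assessed.

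**What to change.** In Operational Definitions, item 6:

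- Delete the sternum from the two-week rule.
- Define delayed healing as skin or subcutaneous wound edges not fully closed, or persistent drainage, two weeks after surgery. The blinded assessor records it at a contact within the planned 30-day follow-up.
- If a sternal item is wanted, report clinical sternal instability or sternal dehiscence without infection within 30 days as its own item. Word it so that it does not overlap criterion [3] of the deep-infection definition, which already includes sternal instability.

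The cost is a reworded definition and a dated entry on the data form. There are two downsides. Fewer delayed-healing events will be counted than under the loose definition. A wound check near day 14 must also fall within follow-up; the protocol text gives no visit dates, so if no contact is planned around then, one would have to be added.

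### The primary outcome is labelled sternal wound complications, but its readmission element counts any surgery-related readmission, whether or not the wound is the cause

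*Protocol*

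**What the plan says.** The Research Question is confined to the wound: "Does application of PRP after CABG, cardiac surgery reduce the frequency of sternal wound complications". The primary outcome carries the same label in the Outcome section, in Operational Definitions item 3 and in the Data Collection Procedure. The Outcome section reads: "Primary outcome will be measured as frequency of sternal wound complications in terms of delayed healing, superficial infection, deep infections, and readmission rate including mediastinitis".

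Item 7 of the Operational Definitions then defines the readmission element: "It is defined as any hospital readmission within 30 days of discharge related to the index surgery". It asks only that the readmission be related to the operation. No section restricts it to wound causes, defines a wound-related subset or says how cause is to be attributed.

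The intervention is local: "Application of 6 mL of autologous PRP to sternum and soft tissue during sternal closure".

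The Protocol does not settle how the elements are combined. The opening summary lists them in the plural: "Wound healing, deep and superficial infection including mediastinitis, and readmissions within 30 days will be documented as primary outcomes". The Data Analysis section lists them as separate variables and names no composite: "Categorical variables (superficial/deep wound infections, delayed healing, readmissions, transfusion requirements, residence".

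**The concern.** The label and the definition describe different things. After coronary bypass a patient can return to hospital for reasons that follow from the operation but have nothing to do with the sternal wound, a rhythm disturbance or an effusion for example. Such a patient meets item 7 and enters the count of sternal wound complications even if the sternum has healed.

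Two consequences follow. First, the rationale in the Introduction is that PRP acts locally on healing and infection. Events outside the wound are therefore expected to be about equally frequent in both arms, and counting them pulls the comparison towards no difference. Second, a difference that arose by chance among non-wound readmissions would be reported as a primary result about the sternal wound.

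**Working it through.** **1. The texts compared.** The research question and outcome label cover sternal wound complications. Item 7 covers all readmissions related to the index surgery, which is a wider set. The difference between the two, surgery-related readmission without a wound cause, counts as a primary event under the current wording.

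**2. Reproducing the planned sample size.** Inputs from the Sample size section: 18% (PRP), 44% (control), 5% significance, 80% power. Sidedness is not stated; two-sided is assumed. With pooled variance and no continuity correction, and mean rate 0.31:

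n = [1.960 × √(2 × 0.31 × 0.69) + 0.842 × √(0.18 × 0.82 + 0.44 × 0.56)]² / 0.26² = (1.282 + 0.528)² / 0.0676 ≈ 48.5, rounded up to 49.

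This matches the stated 49 per group. Power at 49 is 80.4%.

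**3. Dilution if the elements form an any-event composite.** Let p be the rate of wound events and r the rate of non-sternal, surgery-related readmission. Assume r is equal in both arms and independent of wound events. The counted rate is 1 − (1 − p)(1 − r).

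The Protocol gives no value for r, so a range is shown. Its 18% and 44% stand in for p, although they are rates of oedema and infiltration and not of the primary outcome.

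For r = 5%: PRP 1 − 0.82 × 0.95 = 0.221; control 1 − 0.56 × 0.95 = 0.468.
For r = 10%: PRP 1 − 0.82 × 0.90 = 0.262; control 1 − 0.56 × 0.90 = 0.496.

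| r (assumed) | PRP v control | Difference (points) | Risk ratio | Power at 49 per group | n per group for 80% |
|---|---|---|---|---|---|
| 0 | 18.0% v 44.0% | 26.0 | 0.41 | 80.4% | 49 |
| 2% | 19.6% v 45.1% | 25.5 | 0.44 | 77.8% | 52 |
| 5% | 22.1% v 46.8% | 24.7 | 0.47 | 73.7% | 57 |
| 10% | 26.2% v 49.6% | 23.4 | 0.53 | 67.0% | 67 |
| 15% | 30.3% v 52.4% | 22.1 | 0.58 | 60.6% | 77 |
| 20% | 34.4% v 55.2% | 20.8 | 0.62 | 54.5% | 89 |

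The absolute difference shrinks only by the factor (1 − r); the risk ratio moves more.

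**4. Sensitivity to a lower wound-event rate.** The Introduction gives 0.4% to 8% for sternal complications. Take 8% in control and keep the planning risk ratio (8% × 18/44 = 3.3% in the PRP group). The risk ratio then moves from 0.41 to 0.64 at r = 5% (8.1% v 12.6%) and to 0.75 at r = 10% (12.9% v 17.2%). Relative dilution is larger when wound events are rarer. Power at 49 per group would be only 17% with no dilution, against 11% and 8%, so in that setting dilution is not what limits the trial.

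**5. If the elements are tested separately.** Non-sternal readmissions do not enter the infection or healing comparisons, and the table above does not apply to those. Only the readmission comparison mixes wound and non-wound causes.

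**The case against.** The strongest reply has five parts.

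- **The Objective and the Hypothesis speak of complications without limiting them to the sternal wound.** This is correct, and surgery-related readmission would fit those two statements. It does not fit the Research Question or the label of the primary outcome, which are the terms in which the result will be reported.
- **Dilution of the whole primary outcome presupposes a composite.** This stands. A reader might infer that the primary comparison is bound to be diluted. The opening summary and the Data Analysis section do not support that, because they can equally be read as separate outcomes.
- **The mention of mediastinitis beside readmission could be read as confining readmission to wound causes.** This is weak. It names one cause without excluding others, and in the opening summary mediastinitis is attached to infection while readmissions stand with no cause at all. Attribution of cause could be left to an analysis plan, but here the Protocol has already fixed a definition, and it is the wider one.
- **The documents nowhere say that PRP has no effect on non-sternal readmission.** This stands. A reader might infer that PRP cannot prevent such events. That is only an expectation drawn from local application and the stated rationale.
- **The rates of non-sternal readmission are assumed.** This stands. The figures illustrate the effect and do not estimate it.

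A reader might also infer the same fault in item 5, which covers superficial infection ("All the infections will be considered positive that will involve skin and subcutaneous tissue within the first 30 postoperative days, not reaching the sternum") and names no site. The documents do not support that as a separate fault: the reference to the sternum and the heading of sternal wound complications already imply the site. Nor is there a comparable fault in item 6.

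**Conclusion.** The point holds in a limited form. As written, surgery-related readmissions with no sternal wound cause are counted in an outcome labelled sternal wound complications. This rests on the text alone and is true whether or not the elements are combined.

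The statistical size is conditional. It needs an any-event composite, equal and independent non-sternal readmission in both arms, and an assumed rate for it. With 5% to 10% and the Protocol's 18% v 44% as stand-ins, power at 49 per group falls from 80.4% to about 74% to 67%, and 57 to 67 per group would be needed for 80%. Without a composite the damage is confined to the readmission comparison and to how its result is described. The definition should be corrected; the trial's design is not otherwise affected by this point.

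**What to change.** In Operational Definitions item 7, limit the primary-outcome element to readmission whose main cause is a complication of the sternotomy wound (delayed healing, superficial infection or deep infection). Add a cause-of-readmission field to the proforma, to be judged by the blinded outcome assessor already planned. Report all surgery-related readmissions, whatever their cause, under Other outcomes so that no information is lost.

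The cost is a change of wording and one extra field. The downside is fewer primary events. In a composite the restricted element would add few events beyond the infection and healing elements, since a wound-caused readmission will usually be counted there already. The change is needed under either reading of the primary outcome.
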